Investigational Drug Substance(s)	Durvalumab (MEDI4736)
Study Number	ESR-15-11576
Version Number 5	
Date 05/23/16	

Pilot Study to Evaluate the Anti-tumor Effect of Durvalumab (MEDI4736) in Patients with Squamous Cell Carcinoma of the Head and Neck (SCCHN), Human Papilloma Virus (HPV) Positive versus Negative, when Treated Before Surgery

CLINICALTRIALS.GOV: NCT02827838

PROTOCOL SYNOPSIS

Clinical Protocol CCCWFU 60116

Study Title: Pilot Study to Evaluate the Anti-tumor Effect of Durvalumab (MEDI4736) in Patients with Squamous Cell Carcinoma of the Head and Neck (SCCHN), Human Papilloma Virus (HPV) Positive versus Negative, when Treated Before Surgery

Protocol Number:

Clinical Phase: Pilot Study

Study Duration: 18 mo

Investigational Product and Reference Therapy:

Durvalumab will be supplied in glass vials containing 500 mg of liquid solution at a concentration of 50 mg/mL for intravenous (IV) administration.

Research Hypothesis

We hypothesize that immunotherapy with PD-L1 antibody will lead to more intense and efficient specific immune activation against the SCCHN tumor in HPV + patients compared with HPV - patients. We also hypothesize that an extensive analysis of the blood and saliva might lead to identification of markers predictive of a more efficient response to PD-L1 inhibition. Lastly, we hypothesize that a corresponding increase in the immune response with an increase in the number of infiltrative activated immune cells could be associated with an increase in metabolic activity measured by PET SUV. Similarly, an effective anti-tumor activity of the activated immune response could lead to decreased metabolic activity. We are interested in evaluating the dynamic in the metabolic activity early in the treatment and to attempt to detect potential consistency that could be used in future therapeutic paradigms.

Objectives:

Primary Objectives:

The primary objective of this study is to investigate the effect of Durvalumab on local and systemic immune activation by HPV status in patients with oral cavity and oropharynx SCCHN. This will be done by:

- a) Examining the effects of Durvalumab on systemic immune response to HPV and tumor associated antigens
- b) Examining the effects of Durvalumab on immune regulatory mechanisms.
- c) Exploring the association between levels of immune-regulatory miR in plasma and saliva and immune response.

Results will be compared between HPV positive and negative patients to identify a possible differential effect of treatment with Durvalumab. Level of local immune response in the primary tumor and in the regional lymph nodes will be compared whenever possible.

Secondary Objectives:

Investigate the effect of the treatment with Durvalumab on the CT scan and PET scan response.

Evaluate the safety of a short induction treatment with Durvalumab.

Study Design:

This is a non-randomized, open label, uncontrolled, single group assignment study, to evaluate the antitumor effect of Durvalumab in patients with SCCHN when given in a short treatment course before surgery.

10 HPV positive and 10 HPV negative patients will be enrolled, who have an interval longer then 3 weeks between the time of diagnosis and time of surgery.

Two administrations of Durvalumab will be given with an interval of 3 to 17 days between the last administration of drug and surgery. Patients will then undergo surgery as scheduled. After surgery the patients may proceed with adjuvant treatment as indicated by the stage of their disease and by the surgical pathology findings. A Radiation Oncologist is included in the study team in order to address and to include in the therapeutic algorithm the impact of the potential cytoreduction by Durvalumab therapy on the final surgical and pathologic staging.

The primary goal of this pilot study is to make use of biopsy tissue obtained before treatment and of the surgical tissue specimen obtained after treatment with durvalumab, in order to assess tissue biomarkers. Saliva and blood will be collected before each treatment, one week after the treatment and before surgery, and will be analyzed in the same time with tumor tissue.

CT scan or MRI and whenever possible PET scan will be performed before treatment with Durvalumab and before surgery.

The clinical trial will be considered completed as soon as the last patient has completed his last follow up visit, at 1 month after surgical treatment.

Number of Centers: 1

Number of Subjects:

20 patients, 10 patients with HPV positive and 10 patients with HPV negative.

Study Population:

HNSCC of the oral cavity or oropharynx

Inclusion Criteria:

- Histologically or cytologically confirmed SCCHN of the oral cavity (OC; more than 90% patients have HPV negative cancer) or oropharynx (about 60-70% of patient have HPV positive cancer).
- Presence of radiologically or clinically documented disease. All radiology studies must be performed within 28 days prior to registration.
- Any stage, considered candidates for surgery and scheduled for surgery either by robotic or by standard surgical technique.
- Documentation of HPV tested by PCR.
- Willing to provide consent for an additional tissue biopsy for research purposes, to allow a part of their surgical tumor tissue to be utilized for research, and to donate samples of blood and saliva collected before and after treatment.
- All patients must have provided informed consent for correlative studies.
- ECOG performance status of 0 or 1.
- Previous surgery is permitted provided that a minimum of 28 days (4 weeks) have elapsed between any major surgery and date of registration, and that wound healing has occurred.
- Organ and marrow function as defined below:
 - Absolute neutrophil count (ANC) $\geq 1.5 \times 10^{9}/L$;
 - Platelet count $\geq 100 \text{ x } 10^9/\text{L};$

• Hemoglobin \geq 9.0 g/dL;

- Serum bilirubin ≤ 1.5 x ULN (institutional upper limit of normal). Total Bilirubin is less than or equal to ULN, except the case in which the elevated total bilirubin is not a sign of liver disease, such as the Gilbert Syndrome, in which case a Total Bilirubin less than or equal to 2X ULN is acceptable;
- AST and ALT \leq 2.5 x ULN;
- Serum creatinine CL>40 mL/min by the Cockcroft-Gault formula (Cockcroft and Gault 1976) or by 24-hour urine collection for determination of creatinine clearance:

Males:

Creatinine CL=Weight (kg) x (140 - Age)(mL/min)72 x serum creatinine (mg/dL)

Females:

Creatinine CL=Weight (kg) x (140 - Age)x 0.85(mL/min)72 x serum creatinine (mg/dL)

- Female subjects must either be of non-reproductive potential (ie, post-menopausal by history: ≥60 years old and no menses for ≥1 year without an alternative medical cause; OR history of hysterectomy, OR history of bilateral tubal ligation, OR history of bilateral oophorectomy) or must have a negative serum pregnancy test upon study entry.
- In accordance with NCIC CTG policy, protocol treatment is to begin within 2 working days of patient registration
- Written informed consent and any locally-required authorization (e.g., HIPAA in the USA, EU Data Privacy Directive in the EU) obtained from the subject prior to performing any protocol-related procedures, including screening evaluations.
- Age \geq 18 years at time of study entry.
- Subject is willing and able to comply with the protocol for the duration of the study including undergoing treatment and scheduled visits and examinations including follow up.

Exclusion Criteria:

• Involvement in the planning and/or conduct of the study (applies to both AstraZeneca staff and/or staff at the study site). Previous enrolment in the present study.

- Participation in another clinical study with an investigational product during the last 3 mo
- Any previous treatment with a PD1 or PD-L1 inhibitor, including Durvalumab
- Any anti-cancer therapy (chemotherapy, immunotherapy, endocrine therapy, targeted therapy, biologic therapy, tumor embolization, monoclonal antibodies, other investigational agent) within the last 3 months before the first dose of Durvalumab.
- Mean QT interval corrected for heart rate (QTc) ≥470 ms calculated from 3 electrocardiograms (ECGs) using Frediricia's Correction
- Current or prior use of immunosuppressive medication within 28 days before the first dose of durvalumab, with the exceptions of intranasal and inhaled corticosteroids or systemic corticosteroids at physiological doses, which are not to exceed 10 mg/day of prednisone, or an equivalent corticosteroid
- Any unresolved toxicity (>CTCAE grade \geq 2) from previous anti-cancer therapy. Subjects with irreversible toxicity that is not reasonably expected to be exacerbated by the investigational product may be included (e.g., hearing loss, peripherally neuropathy).
- Any prior Grade ≥3 immune-related adverse event (irAE) while receiving any previous immunotherapy agent, or any unresolved irAE >Grade 1
- Active or prior documented autoimmune disease within the past 2 years NOTE: Subjects with vitiligo, Grave's disease, or psoriasis not requiring systemic treatment (within the past 2 years) are not excluded.
- Active or prior documented inflammatory bowel disease (e.g., Crohn's disease, ulcerative colitis)
- History of primary immunodeficiency
- History of allogeneic organ transplant
- History of hypersensitivity to durvalumab or any excipient
- History of pneumonitis or interstitial lung disease
- Subjects with uncontrolled seizures
- Uncontrolled intercurrent illness including, but not limited to, ongoing or active infection, symptomatic congestive heart failure, uncontrolled hypertension, unstable angina pectoris, cardiac arrhythmia, active peptic ulcer disease or gastritis, active bleeding diatheses including any subject known to have evidence of acute or chronic hepatitis B, hepatitis C or human immunodeficiency

virus (HIV), or psychiatric illness/social situations that would limit compliance with study requirements or compromise the ability of the subject to give written informed consent

- Known history of active tuberculosis
- Receipt of live attenuated vaccination within 30 days prior to study entry or within 30 days of receiving durvalumab
- Female subjects who are pregnant, breast-feeding or male or female patients of reproductive potential who are not employing an effective method of birth control
- Patients with body weight < 30kg
- Any condition that, in the opinion of the investigator, would interfere with evaluation of study treatment or interpretation of patient safety or study results

Investigational Product(s), Dose and Mode of Administration:

Durvalumab, 750 mg Q2W (equivalent of 10 mg/kg Q2W) IV infusion x 2 administrations. In exceptional cases in which the window time to surgery is longer than 4 weeks, a third dose of Durvalumab of 750 mg IV infusion is allowed.

Study Assessments and Criteria for Evaluation:

Immune Response Assessments:

- a) Peripheral blood mononuclear cell interferon-γ production *in vitro* (ELISA) in response to commercially available peptide pools corresponding to HPV, p53, Mage-A3, Her2/neu, and survivin will be determined. Responses of patients whose tumor are HPV+ will be compared to those that are HPV-.
- b) PD-1+CD4+, PD 1+CD8+, PD-1L+, and Foxp3+CD4+ tumor-infiltrating cells will be quantified (0 to 3+) using standing immunofluorescence techniques.
- c) The following immune effector and regulatory responses will be assessed in blood using standard flow cytometric techniques: CD4+, CD8+, CD4+FoxP3+ Treg, and CD45RO+CD4+ memory T cells; CD3-CD56+ NK cells, and CD14-HLA-DR-CD15+ MDSC. The results of patients whose tumor are HPV+ will be compared to those that are HPV-.
- d) The relationship between levels of the miRs and the immune response to HPV, immune response to tumor associated antigens, and immune regulatory molecules/cells will be assessed.

Safety Assessments:

- a) Clinical toxicity per NCI Common Terminology Criteria for Adverse Events version 4.0 and
- b) Any delays in planned surgery.

Efficacy Assessments:

Response to Durvalumab using CT scan and PET scan

Statistical Methods and Data Anlaysis:

For this pilot study our goal is to get preliminary descriptive data for a series of measures taken using blood, saliva and tumor tissue pre- and post- immunotherapy. With a sample size of 10 patients in each group (i.e. 10 with HPV+ and 10 HPV-) we will be able to estimate a 95% confidence interval for each group with confidence limits +/- 0.72 standard deviations. We can also examine the change in each measure (pre- versus post- therapy) to see whether any confidence intervals show a significant change from baseline (i.e., the measure increased (or decreased) by more than 0.72 standard deviations). This data would provide useful preliminary information concerning the potential mean value and variability for each measure of interest. It may also provide information about which possible measures are most impacted by the intervention within each group (HPV+/HPV-). Furthermore, if we were to compare groups, we would have 80% power to detect a difference in measures equal to 1.3 standard deviations of the measure of interest using a 2-sample t-test with alpha=0.05.

SCHEDULE OF STUDY ASSESSMENTS

Schedule of study assessments: Screening and Treatment Period

			All assessments	to be perfo	med pre-infusion	unless stated	otherwise	
Assessments to be performed at the times stipulated in the table and as clinically required in the management of the subject.	Pre-screening for PD-L1 status ONLY	Screening	Baseline First drug administration	Follow up	Second Drug Administration	Follow up	Before Surgery (3-17 days from last drug adm.)	Surgery
Day	-42 to -1	-28 to -1		Da	y 1 of the week (=	±3 days)		
Week	-6 to -1	-4 to -1	1	2	3	4		
Written informed consent/assignment of subject identification number	X							
Preliminary eligibility fulfilment (investigator's opinion)	Х							
Demography and history of tobacco and alcohol use		Х						
Previous treatments for SCCHN		Х						
HPV by PCR in FFPE	Xa							
Obtain archived or fresh tumour biopsy for PD-L1 assay, if applicable	X							
Formal verification of eligibility criteria		Х						
Medical and surgical history		Х						
Hepatitis A antibody Hepatitis B surface Ag, Hepatitis C antibody and HIV		Х						
Urine hCG or serum βhCG ^b		Х	As clinically indicated					
Durvalumab administration (monotherapy)			X		X			
Physical examination ^c		X	X	Х	X	X	X	

			All assessments	to be perfo	rmed pre-infusion	unless stated	otherwise	
Assessments to be performed at the times stipulated in the table and as clinically required in the management of the subject.	Pre-screening for PD-L1 status ONLY	Screening	Baseline First drug administration	Follow up	Second Drug Administration	Follow up	Before Surgery (3-17 days from last drug adm.)	Surgery
Day	-42 to -1 -28 to -1 Day 1 of the week (±3 days)							
Week	-6 to -1	-4 to -1	1	2	3	4		
Vital signs (pre- during and post-infusion vital signs assessments) ^d		Х	X	Х	X	Х	Х	
Weight		Х	Х	Х	X	Х	X	
Electrocardiogram ^e		Х	Х				X	
Adverse event/serious adverse event assessment	X ¹	Х	X	X All visits				
Concomitant medications		Х	X All visits					
ECOG performance status		Х	Х	Х	X	Х	X	
Liver enzyme panel ^f		Х	Х	Х	X	Х	X	
Serum Chemistry		Х	Х	Х	X	Х	X	
Magnesium ^f		Х	Х		As clinic	ally indicated		
Uric Acid ^f		Х	X As clinically indicated					
LDH		Х	X	Х	X	Х	X	
Amilase, Lipase		Х	Х	Х	X	Х	X	
Thyroid function tests (TSH and fT3 and $fT4)^{g}$		Х	X	Х	x	Х	X	
Hematology ^f		Х	X					

Schedule of study assessments: Screening and Treatment Period

			All assessments	to be perfo	rmed pre-infusion	unless stated	otherwise	
Assessments to be performed at the times stipulated in the table and as clinically required in the management of the subject.	Pre-screening for PD-L1 status ONLY	Screening	Baseline First drug administration	Follow up	Second Drug Administration	Follow up	Before Surgery (3-17 days from last drug adm.)	Surgery
Day	-42 to -1	-28 to -1		Da	ay 1 of the week (±	⊧3 days)		
Week	-6 to -1	-4 to -1	1	2	3	4		
Urinalysis ^h		Х			As clinically indi	cted		
Coagulation parameters ⁱ		Х			As clinically indi	cted		
Tumor assessment (CT or MRI) ^j		Х					X	
Tumor Assessment PET scan ^k		Х					X	
Immune response assessment (blood)			X	Х	X	X	X	
Blood collection for miRNA			X	Х	X	Х	X	
Saliva collection for miRNA			X	Х	X	X	X	
Whole blood collection for flow cytometry			X				X	
Collect fresh tumor tissue by biopsy and store in Tumor Tissue Bank		Х						
Collect fresh tumor tissue from surgical specimen and store in Tumor Tissue Bank								Х
sPD-L1 concentration (to assess target engagement), if applicable (if additional funding secured)			X		x		X	

Schedule of study assessments: Screening and Treatment Period

^a Should be obtained from the initial diagnostic biopsy. In exceptional cases when not enough tissue is available, it can be performed on tissue obtained with research biopsy or on the surgical specimen. This option is not available when one of the study arms completed accrual. HPV status must be known before at time of screening.

^b Pre-menopausal female subjects of childbearing potential only

Clinical Study Protocol Drug Substance Durvalumab (MEDI4736) Study Number **ESR-15-11576** Edition Number 5 Date 05/23/16 WFU Date 05/18/21

^c Full physical examination at baseline; targeted physical examination at other timepoints

^d Subjects will have their blood pressure and pulse measured before, during and after the infusion at the following times (based on a 60-minute infusion):

- At the beginning of the infusion (at 0 minutes)
- At 30 minutes during the infusion (±5 minutes)
- At the end of the infusion (at 60 minutes ± 5 minutes)
- In the 1 hour observation period post-infusion: 30 and 60 minutes after the infusion (ie, 90 and 120 minutes from the start of the infusion) (±5 minutes) for the first infusion only and then for subsequent infusions as clinically indicated
- If the infusion takes longer than 60 minutes then blood pressure and pulse measurements should be collected every 30 minutes (±5 minutes) and as described above or more frequently if clinically indicated.

^e ECG during screening and at Day1 –baseline. Thereafter as clinically indicated. Baseline and abnormal ECG at any time in triplicate others single. 1 ECG is needed while on treatment, and as clinically indicated. ECGs should be taken within an hour prior to the start of the infusion and at least one time point 0 to 3 hours after the infusion.

^f If screening laboratory assessments are performed within 3 days prior to Day 1 they do not need to be repeated at Day 1. Results for safety bloods must be available and reviewed before commencing an infusion. Creatinine clearance, gamma glutamyltransferase, magnesium, and uric acid testing are to be performed at screening, on Day 1 (unless screening laboratory assessments are performed within 3 days prior to Day 1), and if clinically indicated.

^g Free T3 and free T4 will only be measured if TSH is abnormal. They should also be measured if there is clinical suspicion of an adverse event related to the endocrine system. ^h Urinalysis performed at Screening, Day 1, and as clinically indicated.

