3. STUDY DESIGN

3.1 Overview of study design

This is a non-randomized, open label, uncontrolled, single group assignment study, to evaluate the anti-tumor effect of Durvalumab in patients with HNSCC when given as a short treatment course before surgery.

A schematic diagram of the overall study design is shown below.

Patients must be scheduled for surgery and have a window of at least 3 weeks between the time of diagnosis and time of surgery.

In order to be eligible for this clinical study, the patients must have fresh tumor tissue frozen and saved in our Tumor Tissue Bank or need to consent for an additional biopsy procedure to obtain a tumor tissue sample for the clinical protocol that will be saved in our Tumor Tissue Bank for the correlative studies. Patients will undergo an assessment on their tumor tissue sample to determine HPV status.

10 HPV+ and 10 HPV- patients will be initially enrolled and need to complete the study. If any patient does not complete the study treatment and investigations, the patient will be replaced.

First administration of Durvalumab will be given with the first visit after registration with the clinical study. Second administration of Durvalumab will be given 2 weeks later. An interval of 3 to 17 days must be ensured for all patients between the last administration of drug and surgery. A 7-14 days interval will be strongly considered and attempted in each case. In the rare circumstances in which surgery was scheduled or delayed at more than 2 weeks after second administration of Durvalumab, a third administration of drug must be given in order to ensure the proposed interval between the last dose of Durvalumab and surgery.

After surgery the patients may proceed with adjuvant treatment as indicated by the stage of their disease and by the surgical pathology findings. A Radiation Oncologist is included in the study team in order to address and to include in the therapeutic algorithm the impact of the potential cytoreduction by Durvalumab therapy on the final surgical and pathologic staging.

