4. SUBJECT SELECTION

4.1 Inclusion criteria

For inclusion in the study subjects must fulfill all of the following criteria:

- Histologically or cytologically confirmed HNSCC of the oral cavity (OC; more than 90% patients have HPV negative cancer) or oropharynx (about 60-80% of patient have HPV positive cancer).
- Presence of radiologically or clinically documented disease. All radiology studies must be performed within 28 days prior to registration.
- Any stage, considered candidates for surgery and planned for surgery either by robotic or by standard surgical technique.
- Documentation of HPV tested by PCR (resulted or pending).
- Willing to provide consent for an additional tissue biopsy for research purposes, to allow a part of their surgical tumor tissue to be utilized for research (in case tumor tissue has not already been saved in the Tumor Tissue Bank), and to donate samples of blood and saliva collected weekly through the treatment.
- All patients must have provided informed consent for correlative studies.
- ECOG performance status of 0, 1 or 2.
- Patients must have no prior exposure to immune-mediated therapy, including anti-CTLA-4, anti-PD-1, anti-PD-L1, or anti-programmed cell death ligand 2 antibodies, excluding therapeutic anticancer vaccines.
- At least 1 lesion, not previously irradiated, that can be accurately measured at baseline as ≥10 mm in the longest diameter (except lymph nodes, which must have a short axis ≥15 mm) with CT or MRI or clinical measurement and that is suitable for accurate repeated measurements as per RECIST 1.1 guidelines.
- Previous surgery is permitted provided that a minimum of 28 days (4 weeks) have elapsed between any major surgery and date of registration, and that wound healing has occurred.

Clinical Study Protocol Drug Substance Durvalumab (MEDI4736) Study Number **ESR-15-11576** Edition Number 5 Date 05/23/16 WFU Date 03/31/17

- Organ and marrow function as defined below:
 - Absolute neutrophil count (ANC) $\geq 1.5 \times 10^{9}/L$;
 - Platelet count $\geq 100 \times 10^9$ /L;
 - Hemoglobin \geq 9.0 g/dL;
 - Serum bilirubin ≤ 1.5 x ULN (institutional upper limit of normal)
 - Total Bilirubin is less than or equal to ULN, except the case in which the elevated total bilirubin is not a sign of liver disease, such as the Gilbert Syndrome, in which case a Total Bilirubin less than or equal to 2X ULN is acceptable.
 - AST and ALT \leq 2.5 x ULN;

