8.1.1 Screening Phase

The procedures for the pre-screening, screening, and treatment periods in this study presented in the Schedule of Assessments table.

Screening procedures will be performed up to 28 days before Day 1, unless otherwise specified. All subjects must first read, understand, and sign the IRB/REB/IEC-approved ICF before any study-specific screening procedures are performed. After signing the ICF, completing all screening procedures, and being deemed eligible for entry, subjects will be enrolled in the study. Procedures that are performed prior to the signing of the ICF and are considered standard of care may be used as screening assessments if they fall within the 28-day screening window.

The following procedures will be performed during the Screening Visit:

Clinical Study Protocol Drug Substance Durvalumab (MEDI4736) Study Number **ESR-15-11576** Edition Number 5 Date 05/23/16 WFU Date 03/31/17

- Informed Consent
- Review of eligibility criteria
- Medical history and demographics
- Complete physical exam
- ECOG Performance Status
- Vitals signs, weight and height
- 12-lead ECG (in triplicate [2-5 minutes apart])
- Tumor biopsy
- HPV by PCR in tumor tissue (can be pending at the time of enrollment if none of the arms have met the 10 patients enrollment requirement)
- Review of prior/concomitant medications
- Imaging by CT or MRI (+/- PET)
- Clinical laboratory tests for:
 - Hematology (see Table 3)
 - Clinical chemistry (see Table 4)
 - o TSH
 - Coagulation (PT, PTT, INR)
 - Creatinine Clearance
 - Serum pregnancy test (for women of childbearing potential only)
 - Hepatitis serologies
 - Urinalysis (see Table 5)

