8.3.4 Fresh tumor biopsies

Procurement of a fresh tumor sample before treatment is mandatory for enrolling the patient in this study, unless a tumor sample has already been banked in our Tumor Tissue Bank at the time of initial diagnostic biopsy, under Wake Forest University IRB approved and monitored Protocol Number BG98-391.

A separate consent for banking tumor tissue is available for all patients undergoing biopsies and surgeries at our institution.

Due to tumor location in the study patient population (oral cavity and oropharynx) biopsies will be performed in the office. However, if needed in exceptional cases, procedure will be scheduled in OR. One tumor sample and one normal tissue sample will be collected by incisional biopsy under local anaesthesia by our co-PI investigator, [name] of ENT or his designee.

Biopsy tissue will be placed immediately in special tubes containing transporting media, readily available and [name], tissue procurement officer, will be called in advance and will transport the tissue to our Tumor Tissue Bank where the sample will be flash frozen and stored.

Additional samples of fresh primary tumor tissue and adjacent normal tissue as well as sample of tumor involved lymph node tissue (whenever the case) will be collected for the same patient from the surgical

specimen obtained at the time of surgery, after conclusion of the treatment with Durvalumab. [name] will be informed in advance about the time of surgery and she will attend the surgical specimen in the Department of Pathology, collect the specimens with the help of the Pathologist on call and transport the specimen to the Tumor Tissue Bank where it will be fresh frozen and stored.

Tissue collection will be monitored by the IRB under the current protocol, including maintenance of patient confidentiality and the HIPAA-compliant sample database. The tissue as well as blood samples are kept in the Tumor Tissue Core Laboratory of the 4th floor of the Hanes Building, which is either manned by a member of the Tumor Tissue Core Laboratory or is locked at all times. The Core Lab's database resides on the Comprehensive Cancer Center of Wake Forest University's (CCCWFU) secure server behind the WFUHS firewall with HIPAA-compliant security. The database is only accessible by the Tumor Tissue Core personnel.

Fresh frozen tissue collected before and after treatment will be used for the following assays for the following immune assessments:

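### In exceptional cases the HPV group may be assigned from tissue taken after durvalumab; it should come from pre-treatment tissue only

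*Combined protocol and SAP*

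**What the plan says.** Footnote a of the Schedule of Study Assessments names the initial diagnostic biopsy as the source for HPV PCR and then allows an exception: "In exceptional cases when not enough tissue is available, it can be performed on tissue obtained with research biopsy or on the surgical specimen". It continues: "This option is not available when one of the study arms completed accrual. HPV status must be known before at time of screening".

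Other sections bear on when the label becomes known and on which tissue:

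- Section 4.1 requires "Documentation of HPV tested by PCR (resulted or pending" (so a result need not be in hand). Appendix 3 agrees. The synopsis version of the same criterion does not mention a pending result.
- Section 8.1.1 says that the result "can be pending at the time of enrollment if none of the arms have met the 10 patients enrollment requirement".
- Section 8.3.4 describes the surgical tissue as a "specimen obtained at the time of surgery, after conclusion of the treatment with Durvalumab". The same section states: "Procurement of a fresh tumor sample before treatment is mandatory for enrolling the patient in this study", unless tumor has already been banked.
- Section 3.1 provides for a radiation oncologist to address "the impact of the potential cytoreduction by Durvalumab therapy on the final surgical and pathologic staging".

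Sections 11.1 to 11.3 compare HPV-positive with HPV-negative patients on every primary and imaging endpoint. They give no rule for an undeterminable HPV result, no flag for a label obtained from post-treatment tissue, and no sensitivity analysis.

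**The concern.** HPV status is the only grouping variable in this non-randomized study. A variable that defines the groups should be fixed before exposure, so that treatment cannot influence who is counted where. Footnote a allows a patient to be enrolled, treated, operated on and only then assigned to a group.

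If durvalumab has reduced the tumor, PCR on what remains could fail or be falsely negative. A failed PCR leaves the patient without a group. A false negative can occur only in a patient who is truly HPV-positive, and it is plausibly more likely where the tumor has shrunk most. Such an error lowers the HPV-positive mean, raises the HPV-negative mean, and works against the hypothesis in section 1.3 of stronger activation in HPV-positive patients. With 10 patients per group, one wrong label is enough to matter.

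**Working it through.** **Inputs.** Section 11.3 gives 10 patients per group, a difference of 1.3 SD, a 2-sample t-test, alpha 0.05, 80% power, and 95% confidence limits of ±0.72 SD per group. I take the test as two-sided. The number of mislabelled patients, k, is not in the documents, so I assume it and show a range.

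**1. The plan's own figures.**
- Half-width: t(0.975, 9)/√10 = 0.715 SD, which matches 0.72.
- Power from the noncentral t, 10 against 10, 1.3 SD: 78.5%, close to the stated 80% (exactly 80% needs 1.32 SD).

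**2. Random mislabelling, labelled groups kept at 10 and 10.** If k of the 10 patients labelled HPV-negative are truly positive, the expected difference is 1.3 × (1 − k/10). Power for k = 1 to 3 is from 100,000 simulated trials per case.

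| k | Expected difference (SD) | Power |
|---|---|---|
| 0 | 1.30 | 78.5% |
| 1 | 1.17 | about 67% |
| 2 | 1.04 | about 54% |
| 3 | 0.91 | about 42% |

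If one patient moves across and the groups become 9 and 11, the difference is 13/11 = 1.18 SD, and power is again about 67%.

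**3. Mislabelling that depends on response.** Suppose the patient with the greatest tumor clearance among 10 true positives is the one mislabelled, and clearance correlates ρ with the immune endpoint. The expected maximum of 10 standard normal values is 1.539. With the HPV-positive mean set at 0 and the HPV-negative mean at −1.3:

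- mean of the 9 remaining positives: −1.539ρ/9
- mean of the 11 labelled negative: (−13 + 1.539ρ)/11
- difference: 13/11 − 1.539ρ(1/9 + 1/11) = 1.182 − 0.311ρ

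This gives 1.18 SD at ρ = 0, 1.09 at 0.3, 1.03 at 0.5 and 0.87 at 1.

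**4. Label lost, patient not replaced.** With 9 against 10 at 1.3 SD, power is 76.0%; with 8 against 10, 73.0%; with 7 against 10, 69.4%. Losing a label costs much less than getting one wrong.

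**5. Whether the exception is needed.** Footnote a already accepts the research biopsy. Section 8.3.4 makes a pre-treatment tumor sample mandatory, and the efficacy set in section 11.1.2 requires tissue from before treatment. A patient with no pre-treatment tissue would therefore be outside the efficacy set in any case. One gap remains: the schedule specifies PCR on formalin-fixed, paraffin-embedded tissue, while section 8.3.4 has the research sample flash frozen. A patient could have the mandatory sample and still lack material in the specified form.

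**The case against.** The strongest reply is that the route is narrow. It is reserved for exceptional cases and closes once either group is full. Harm then needs inadequate diagnostic tissue, an unusable research biopsy, a truly HPV-positive tumor, and enough clearance to make PCR fail. Section 1.5.2 reports a response rate of only 11% in unselected SCCHN, and section 9.1.1 warns that response may be delayed. This stands as a limit on how often the problem can arise. It does not remove the permission, and the analysis sections contain nothing that would catch a bad label.

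Four stronger readings are tempting and are not supported:

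- **That footnote a flatly contradicts itself.** Its last sentence, "HPV status must be known before at time of screening", conflicts with the surgical-specimen option only if read alone. Read after the sentence about completed accrual, it can apply only once a group is full, which fits sections 4.1 and 8.1.1. The wording needs reconciling, but on that reading late labelling is a deliberate permission.
- **That a pending result means post-treatment tissue.** Section 8.1.1 lists biopsy and PCR as screening procedures. Under section 4.1 treatment starts within 2 working days of registration, so laboratory turnaround on pre-treatment tissue explains a pending result equally well.
- **That durvalumab is known to change HPV results.** No passage says so. The mechanism is inferred from the remark on cytoreduction, which concerns staging.
- **That pending patients are likely to overfill a group.** This would need several pending at once. At one patient a month (section 13.2) and 17 to 31 days from first dose to surgery (14 days plus 3 to 17), Poisson arrivals give a 2–8% chance of three or more enrolments in that window, even if every patient were pending. An overfilled group also costs resources without biasing the contrast.

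**Conclusion.** The point holds in a limited form. The plan permits, rarely and only while both groups are open, the grouping variable to be measured after treatment, and it does not flag or handle such labels. The likely consequence is dilution of the HPV contrast.

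For one mislabelled patient, a realistic illustration is an expected difference of 1.03 to 1.18 SD instead of 1.30 SD. The figure of 0.87 SD is an extreme, because it needs perfect correlation between tumor clearance and the immune endpoint, which nothing in the documents supports. All these sizes rest on an assumed count of wrong labels and on the plan's own 1.3 SD. Because this is a descriptive pilot and the event should be rare, the change is a cheap improvement; the point does not invalidate the design.

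**What to change.** In footnote a, remove the permission to use the surgical specimen. State that the HPV group is assigned only from tissue taken before the first infusion: diagnostic biopsy, research biopsy or banked pre-treatment tissue. In addition:

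- Say which pre-treatment material is acceptable for the PCR, given that the schedule specifies paraffin-embedded tissue and the research sample is flash frozen.
- Define a pending result as one outstanding on pre-treatment tissue, and reconcile the footnote's last sentence with sections 4.1 and 8.1.1 and with the synopsis criterion.
- Add to section 11 that a patient whose pre-treatment PCR fails is left out of the HPV comparison and replaced. Such a patient, if dosed, stays in the safety set under section 11.1.1.
- Treat any PCR on surgical tissue as descriptive; it never assigns or changes the group.

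The cost is a short amendment. A rare patient without usable pre-treatment tissue for PCR could not be enrolled or would have to be replaced, and a small part of some research samples may be used for the PCR. The planned sample size and the stated power are unchanged.
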